# Efficacy evaluable (EE) Population

The efficacy evaluable (EE) population will consist patients who have received at least one post-baseline disease response assessment. This population will be used for supportive inferences for primary analyses of efficacy.

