# 2.1. GENERAL ANALYSIS METHODS

All summary statistics will be computed and displayed among the corresponding analysis population, and by each scheduled assessment time point whenever applicable. Summary statistics for continuous variables will minimally include n, median, mean, standard deviation, minimum, and maximum. For categorical variables, frequencies and percentages will be presented with the denominators for the percentages determined based on the analysis population used, unless otherwise specified. For time-to-event variables, the Kaplan-Meier method will be used for descriptive summaries. Graphical displays will be provided as appropriate.

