# 3.1.1. Efficacy Populations

# **Modified Intent-to-Treat Population**

The modified intent to treat (mITT) population for Part A, Part B, and Part C will consist of all patients who receive at least one dose of study treatment.

mITT population will be used for primary analyses of efficacy.

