# Per-protocol (PP) Population

The per-protocol (PP) population will consist of all patients who have received at least 2 cycles of study treatment, are compliant with study assessments, have received at least 80% of their prescribed study treatment, and have no major protocol violations that would compromise the assessment of efficacy. Major violations will be determined independently of knowledge of response to therapy, and prior to database lock and study analysis. This population will be used for supportive inferences concerning efficacy, however, if there are major differences between the results in this population and those obtained in the mITT population, this will be taken into consideration in the assessment of efficacy.

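### The supportive efficacy-evaluable (EE) population drops patients who die or progress clinically before any scan, so its response and disease-control rates can only equal or exceed the primary mITT rates

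*SAP*

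**What the plan says.** SAP 3.1.1 sets out three efficacy populations.

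- **mITT**, for Parts A, B and C, "will consist of all patients who receive at least one dose of study treatment". It carries the main result: "mITT population will be used for primary analyses of efficacy".
- **EE** is made up of "patients who have received at least one post-baseline disease response assessment". Its role is stated as follows: "This population will be used for supportive inferences for primary analyses of efficacy". The definition does not mention death, clinical progression or any other outcome before the first assessment. EE is not among the analysis populations in Protocol 9.3.
- **PP** requires "at least 2 cycles of study treatment, are compliant with study assessments, have received at least 80% of their prescribed study treatment", and also the absence of major violations, which are to be judged without knowledge of response. It too is supportive, but of a major difference from mITT the SAP says "this will be taken into consideration in the assessment of efficacy".

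SAP 2.1 has "denominators for the percentages determined based on the analysis population used, unless otherwise specified". SAP Table 4-1 counts CR and PR for ORR, and CR, PR and SD of at least 16 weeks for DCR. Neither Table 4-1 nor SAP 4.2 sets a different denominator.

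**The concern.** An efficacy-evaluable set is usually meant to remove patients whose response is unknown. For a patient who died or deteriorated clinically before a scan, the response is not unknown: treatment failed. The SAP definition nevertheless treats such a patient in the same way as one who simply missed imaging.

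These patients are foreseeable here. The population has exhausted standard options and is progressing at entry. The first scheduled scan is at about week 8 (Protocol 7.3.2.1 and 7.3.3.1). Protocol 5.2 lets the investigator stop treatment for clinical progression. Protocol Appendix 4 recognises discontinuation for deteriorating health without objective progression. The end-of-treatment scan is required only when treatment ends for a reason other than disease progression, which can be read as exempting a patient who has progressed clinically.

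At stake is how the supportive table is read. If EE is above mITT, a reader may take the gap as corroboration, when it measures only the share of patients removed.

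**Working it through.** The plan states no response rate, early-loss rate or expected EE size, so there is no figure of its own to reproduce. The size follows from the definitions.

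**Inputs**
- Treated patients, n: the mITT denominator (SAP 3.1.1).
- Patients counted as CR or PR (ORR), or as CR, PR or SD of at least 16 weeks (DCR): x (SAP Table 4-1).
- Treated patients with no post-baseline assessment: k, and d = k/n. The documents give neither, so d is assumed to lie between 10% and 30%.

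**Step 1: direction.** A patient with no post-baseline assessment cannot be recorded as CR, PR or SD of at least 16 weeks. All k excluded patients therefore come from the n − x who do not count, and x is unchanged:

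- mITT rate = x/n
- EE rate = x/(n − k) = (x/n)/(1 − d)

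Since 1 − d is at most 1, EE is never below mITT. It is strictly above whenever x and k are both at least 1.

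**Step 2: size over the assumed range**
- ORR of 10%: 0.10/0.90 = 11.1%; 0.10/0.70 = 14.3%.
- DCR of 30%: 0.30/0.90 = 33.3%; 0.30/0.70 = 42.9%.

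**Step 3: whole patients.** Part C allows at most 10 patients per dose level (SAP 1.4). With illustrative counts and exact 95% intervals:
- ORR: 1/10 = 10.0% (0.3 to 44.5). With two unscanned patients removed, 1/8 = 12.5% (0.3 to 52.7).
- DCR: 3/10 = 30.0% (6.7 to 65.2). With two removed, 3/8 = 37.5% (8.5 to 75.5).

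**Step 4: consistency within the SAP.** Table 4-2 censors at first dose a patient with no adequate post-baseline assessment, but makes an exception where death comes before the first assessment; such a death is a PFS event. In EE the same death drops out of ORR and DCR altogether.

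**Step 5: PP.** Here the direction is not fixed. Starting from 3/10 with disease control:
- Remove two non-controlled patients: 3/8 = 37.5%.
- Remove one non-controlled patient (fewer than 2 cycles) and one controlled patient (below 80% of treatment, or a major violation): 2/8 = 25.0%, below the mITT 30.0%.

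**The case against.** The strongest reply is that the primary analysis already deals with this. mITT keeps every treated patient, so early deaths and failures stay in its denominator, and EE is labelled supportive. Protocol 9.4.1 tabulates the number in each population, so the shrinkage would be visible. No stated decision rests on EE: the futility rule uses the first ten patients at the RP2D (Protocol 9.5.1), and the RP2D is declared on safety and tolerability (Protocol 2.1.1). With 10 patients, the exact interval is far wider than the shift. All of this stands, and it limits the point to a small one. It does not change the fact that EE can move in only one direction.

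Four stronger readings are tempting, and the documents do not support them.

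- *EE loses everyone who stops before week 8.* It requires one assessment at any time. A patient stopping early for toxicity should have an end-of-treatment scan (Protocol 7.3.3.1) and would then be in EE, as would a patient with an early unscheduled scan showing progression. The relevant d is the share never scanned, not the share leaving early.
- *PP rates rise by construction.* The 2-cycle rule pushes that way, but the dosing, assessment-compliance and violation criteria can also remove responders, as Step 5 shows.
- *PP guarantees about 8 event-free weeks.* SAP 2.5 counts any non-zero dose as being treated in a cycle, so one dose in Cycle 2, from about Day 29, could satisfy the rule. SAP 1.5 also allows treatment after objective progression.
- *The bias carries into the efficacy conclusion.* The sentence on taking differences into account concerns PP, not EE, and only major differences. It does not say that PP overrides mITT.

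**Conclusion.** The point holds for EE and is modest. As defined, EE ORR and DCR equal the mITT rates multiplied by 1/(1 − d), so agreement or improvement in EE carries no independent information about efficacy. For an assumed d of 10% to 30%, the multiplier is 1.11 to 1.43: an ORR of 10% reads as 11.1% to 14.3%, and a DCR of 30% as 33% to 43%. The direction rests only on the SAP's definitions and its denominator rule. The size rests on d, which the documents do not give.

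The primary mITT rates are not inflated. A rise in PP is likely but not certain, and there is no sufficient reason to redefine PP: waiving its 2-cycle rule would be a choice about what that population is meant to describe, not the correction of an error.

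**What to change.** In SAP 3.1.1, define EE as patients with at least one post-baseline disease response assessment, or who died or discontinued for clinical or disease progression before having one. State that the second group counts as non-responders for ORR and DCR. Patients who are unscanned for other reasons, such as withdrawal, would still be left out, so EE keeps its purpose.

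In the 3/10 DCR example with two unscanned patients, if both had died early, EE would return to 3/10 = 30.0%. If one had died and one had withdrawn, it would be 3/9 = 33.3%.

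Leave the PP definition as it is, but when PP–mITT differences are considered, show the PP exclusions by reason beside the mITT result.

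The cost is one sentence for EE and one added display for PP. The reason for stopping and the date of death are already needed for disposition and PFS. The downside is that EE rates become slightly less favourable and closer to mITT.

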# Per-protocol (PP) Population

The per-protocol (PP) population will consist of all patients who have received at least 2 cycles of study treatment, are compliant with study assessments, have received at least 80% of their prescribed study treatment, and have no major protocol violations that would compromise the assessment of efficacy. Major violations will be determined independently of knowledge of response to therapy, and prior to database lock and study analysis. This population will be used for supportive inferences concerning efficacy, however, if there are major differences between the results in this population and those obtained in the mITT population, this will be taken into consideration in the assessment of efficacy.

# 3.1.2. Safety Population

All patients who receive at least 1 dose of the study treatment will be included in the safety population. All safety analyses will be performed on the safety population.

# **DLT Evaluable Population**

All patients who complete a minimum of 1 cycle of treatment, defined as having received  $\geq$  75% of KPT-9274 doses during Cycle 1 (e.g.,  $\geq$  9 of 12 doses in the 3 doses/week schedule), or who have a DLT within the first cycle of treatment, will be included in the DLT evaluable population.

# 3.2. DEMOGRAPHICS, MEDICAL HISTORY, AND BASELINE CHARACTERISTICS

In general, the baseline value is defined as latest value prior to the first dose of study treatment. Demographics, medical history and baseline characteristics will generally be summarized among mITT and safety populations, unless otherwise specified. P-values on demographic, medical history and baseline characteristic data will not be calculated.

# 3.2.1. Demographic Data

Demographic variables include sex (female, male), race (American Indian or Alaska Native, Asian, Black or African American, White, Other), ethnicity, and age at study entry.

# 3.2.2. Prior Antineoplastic Therapy

Prior antineoplastic therapy will be summarized for the mITT population with the following variables:

- Number of unique medication
- Number of prior regimens of antineoplastic therapy
- Best response of most recent prior antineoplastic regimen
- Days since discontinuation of most recent prior antineoplastic therapy to the start of study treatment, which will be calculated as the date of first study treatment stop date of most recent antineoplastic therapy+1
- Days since most recent disease progression to the start of study treatment

The detailed history of prior systemic therapy including start and end dates of the medication, best response, progression during or after therapy, as well as discontinuations due to, toxicity and/or intolerability may also be provided in a data listing.

# 3.2.3. Medical/Surgical History

Medical history will be summarized in the mITT population by system organ class (SOC) and preferred term (PT) using the number and percentage of patients who have at least one occurrence of a SOC and PT. The summary will be sorted by alphabetic order in SOC, and further by decreasing frequency of PT within each SOC. When more than one PT has the same frequency, the order of presentation will be alphabetical in PTs.

# 3.2.4. Disease History

Disease history will be summarized with below variables:

- Duration from initial diagnosis to the start of study treatment
- Disease stage at initial diagnosis
- Primary tumor location

# 3.2.5. Baseline Characteristics

Baseline characteristics will be summarized including the following variables:

- Baseline height (cm)/ weight (kg)/ body surface area (m²)/ BMI (kg/m²)
- Baseline ECOG performance status
- Number of unique ongoing medical history (Preferred Terms) per patient
- Number of unique ongoing medications (Anatomical Therapeutic Class [ATC] Level 4 and standard name) per patient

# 3.3. CONCOMITANT MEDICATIONS AND PROCEDURES

Concomitant medication consists of any prescription or over-the-counter preparation, including vitamins, dietary supplements, over-the-counter medications, and oral herbal preparations taken during the study, as well as changes in medication. Patients may continue their baseline medication(s). Concomitant medications include any medications used to treat symptoms, concomitant diseases such as diabetes, hypertension, etc., AEs and intercurrent illnesses that are medically necessary as part of standard care. All concomitant medication(s) must be reported on the eCRF. Any diagnostic, therapeutic, or surgical procedure performed during the study period should be recorded, including the dates, description of the procedure(s), and any clinical findings, if applicable. Concomitant medication will generally be summarized among mITT and safety populations, unless otherwise specified.

All medications will be coded using the World Health Organization Drug Dictionary Enhanced (WHO DDE).

# 3.3.1. Prior and Concomitant Medications and Procedures

Prior medications are any treatments received by the patient prior to the first dose of study treatment. Prior medications can be discontinued before first dose of study treatment or can be ongoing during treatment period.

Concomitant medications are any treatments received by the patient concomitantly with study treatment, from first dose of study treatment to last dose of study treatment + 30 days.

Concomitant medications will be summarized according to the WHO DDE by the ATC level 2 (therapeutic level), level 4 (generic level) and standard name. A patient taking the same drug multiple times will only be counted once.

Note that a medication can be classified as both a prior medication and a concomitant medication.

The use of prior and concomitant medications and procedures may also be provided in a data listing.

Please refer to Section 2.2.2 for details on data handling rules related to computation, dates, imputation for missing dates.

# 3.4. EXTENT OF STUDY TREATMENT EXPOSURE AND COMPLIANCE

Study treatment is considered taken when patient actually received any study drug (KPT-9274 and/or niacin and/or nivolumab, partial or complete). Extent of exposure and compliance will generally be summarized among mITT and safety populations, unless otherwise specified.

The extent of exposure for the study treatment will be assessed using the following variable:

• Duration of study treatment exposure

The following will be presented separately for KPT-9274, niacin and nivolumab:

- Duration of exposure
- Total dose received
- Average dose received per week
- Number and percentage of patients with dose reduction
- Number and percentage of patients with dose interruption
- Number and percentage of patients with missed dose

Duration of exposure is defined as the date of last dose - date of first dose + 1.

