6.1.3. Nivolumab (Part C)

Nivolumab will begin on the first day (C1D1) and will be administered through an intravenous (IV) line on Day 1 of each cycle (once every 4-week cycle) at 480 mg according to the current prescribing information. Nivolumab will be given per standard of care.

All dosages prescribed to the patient and all dose changes during the study must be recorded on the eCRF.

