6.2.8.1.2. Dose Holds or Reductions for Nivolumab (Part C)

- Dose reductions are not allowed for nivolumab. Consult the product label for dose holds.

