# DOSE FINDING PHASE

This Arm will treat approximately 20 patients with melanoma who progressed on an anti-PD-1 or anti-PD-L1 antibody in a prior line of therapy. Two dose levels of KPT-9274 (30 and 40 mg) in combination with nivolumab will be tested in parallel. Patients will be enrolled first into the 30 mg cohort. Patients will be treated with 30 or 40 mg KPT-9274 three times a week every other day (Days 1, 3, 5, 8, 10, 12, 15, 17, 19, 22, 24, and 26) during each 28-day cycle in combination with a standard dose and schedule of nivolumab (480 mg on Day 1 of each 28-day cycle). A maximum of 10 patients may be enrolled at each dose level. Treatment will continue until disease progression, unacceptable AEs or toxicity that cannot be managed by supportive care, patient's withdrawal of consent, Investigator decision to discontinue study treatment, pregnancy, death, or Sponsor decision to terminate the study. A safety review committee will evaluate all available data from both cohorts after the last patient enrolled has been observed for at least 2 cycles to determine the RP2D. Additional dose levels (20 mg or 60 mg) might be evaluated if an optimal dose is not identified and the safety review committee is in agreement. The definition of a DLT is the same as described in Parts A and B. Response will be assessed every 8 weeks per RECIST 1.1 criteria.

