# 2.2.1. Handling of Computation of Treatment Duration if Study Treatment End of Treatment Date is Missing

For the calculation of treatment duration, the date of the last dose of study treatment is equal to the date of last study treatment dosing reported on study treatment dosing form. If all the dosing dates are missing, then the duration is missing.

The last dose intake should be clearly identified on the eCRF dosing page and should not be approximated by the last returned package date.

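### SAP 3.4 leaves the 28-day interval after the last nivolumab infusion out of exposure duration and gives no denominator for average weekly dose

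*SAP*

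**What the plan says.** SAP 3.4 introduces its per-drug exposure variables with "The following will be presented separately for KPT-9274, niacin and nivolumab". The list includes duration of exposure, total dose and "Average dose received per week". One definition of duration follows for all three drugs: "Duration of exposure is defined as the date of last dose - date of first dose + 1". SAP 2.2.1 ties the end of treatment to an actual dosing date rather than to the end of a cycle: "the date of the last dose of study treatment is equal to the date of last study treatment dosing reported" on the dosing form. SAP 3.4 also lists, separately, a duration of exposure for study treatment as a whole. It gives no formula for average weekly dose.

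Protocol 6.1.3 schedules nivolumab on "Day 1 of each cycle (once every 4-week cycle) at 480 mg". Protocol 6.2.8.1.2 adds: "Dose reductions are not allowed for nivolumab". For the partner drug, the SAP's Part C design text says: "Patients will be treated with 30 or 40 mg KPT-9274 three times a week every other day". That is 12 doses per 28-day cycle, the last on Day 26.

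Neither document credits the interval after the last infusion. The sponsor's programming rule book is cited in SAP 2.2.2 and 2.2.3 for imputation methods only, so it is not said to fill this gap.

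**The concern.** Counting from first to last dose works tolerably for a drug taken three times a week, because little time is lost after the last tablet. It carries over poorly to an infusion given once every 28 days, where the whole last interval disappears. After one full cycle, a single patient would show 26 days of KPT-9274 and 1 day of nivolumab in the same table, although both drugs were dosed to plan over the same 28 days.

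The undefined weekly dose adds to this. The per-drug duration is the denominator a programmer would most naturally choose. With it, the smallest nivolumab exposures yield the largest apparent weekly doses. SAP 2.1 requires the mean and the maximum, and Part C has at most 10 patients per dose level, so one short-exposure patient could dominate the summary. Part C's primary objective is safety, tolerability and the recommended dose of the combination, and the exposure table is the background against which those data are read.

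**Working it through.** The documents state no exposure figure, so there is nothing to reproduce. The check is direct arithmetic on the definition.

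**Inputs**
- Duration rule: last dose date minus first dose date plus 1 (SAP 3.4).
- Nivolumab: 480 mg every 28 days with no reductions (Protocol 6.1.3 and 6.2.8.1.2), so the planned rate is 480/4 = 120 mg per week.
- KPT-9274 in Part C: 12 doses per cycle, the last on Day 26. At 30 mg the planned rate is 3 × 30 = 90 mg per week.
- Assumption, not in the SAP: average weekly dose = total dose ÷ (duration in days ÷ 7).

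**Nivolumab, k infusions given on time**
- Duration by the SAP rule: 28(k − 1) + 1 days.
- Planned dosing cover: 28k days. The difference is 28k − [28(k − 1) + 1] = 27 days for any k, if the patient is alive and under observation through the last interval.
- Weekly dose with the nivolumab-specific duration: 480k × 7 ÷ [28(k − 1) + 1].
- Weekly dose with the overall duration, taking KPT-9274 through Day 26 of the last cycle: 480k × 7 ÷ [28(k − 1) + 26].

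| Infusions | SAP duration (days) | Planned cover (days) | mg/week, nivolumab duration | Ratio to 120 | mg/week, overall duration | Ratio to 120 |
|---|---|---|---|---|---|---|
| 1 | 1 | 28 | 3,360 | 28.0 | 129.2 | 1.08 |
| 2 | 29 | 56 | 231.7 | 1.93 | 124.4 | 1.04 |
| 3 | 57 | 84 | 176.8 | 1.47 | 122.9 | 1.02 |
| 6 | 141 | 168 | 143.0 | 1.19 | 121.4 | 1.01 |
| 13 | 337 | 364 | 129.6 | 1.08 | 120.7 | 1.01 |

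If weeks were counted from cycles started, the result would be 120 in every row.

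**Effect on a cohort mean (assumed mix).** Take nine patients with three infusions and one patient with one infusion. With the nivolumab-specific duration the mean is (9 × 176.8 + 3,360)/10 = 495 mg per week, about four times plan because of one patient.

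**Effect on a delayed infusion.** Two infusions 56 days apart have an SAP duration of 57 days and a weekly dose of 960 × 7/57 = 117.9 mg, which looks on schedule. With the last interval counted, duration is 56 + 28 = 84 days and weekly dose is 960 × 7/84 = 80 mg, which shows the delay.

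**KPT-9274 at 30 mg, same rule, complete cycles**
- One cycle: 360 × 7/26 = 96.9 mg per week against 90 (ratio 1.08).
- Six cycles: 2,160 × 7/166 = 91.1 mg per week (ratio 1.01).

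Niacin is taken with each KPT-9274 dose, so the timing argument is the same.

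**The case against.** The other side has a good deal to say.

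- **First-to-last-dose time is explicit and reproducible.** It fits the actual-dosing-date rules in SAP 2.2.1 and 2.3. That is true, so this is a choice of definition and not an arithmetic slip. The choice still suits a once-per-28-days drug badly, and a better one is available at almost no cost.
- **The SAP does not say that weekly dose is divided by this duration.** A reader might infer that the plan overstates weekly nivolumab dose as a matter of fact, by up to 28-fold. The documents do not support that. The denominator is missing, and 28-fold is the one-infusion case under one possible choice. The overall study-treatment duration gives about 8% or less when KPT-9274 continues to Day 26, and counting cycles started gives no overstatement.
- **Not every patient is 27 days short.** A patient who dies 10 days after the last infusion is not, and the same holds where data cut-off falls inside the last interval.
- **It is tempting to say that many Part C patients will have only one or two infusions.** Neither document states an expected treatment duration, so that frequency is unknown.
- **The safety analysis proper is untouched.** The treatment period in SAP 2.4 and the adverse-event window in SAP 5.1.1.1 run to 30 days after the last dose or to new antineoplastic treatment, and related events count beyond that. Percentages in SAP 5.1.2 use patient counts, not person-time. Total dose and dose-count compliance are reported alongside, so a 480 mg total would remain visible.

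These objections limit the size of the point. They do not remove the omitted interval or the missing formula.

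**Conclusion.** The concern holds in a limited form. Without any further assumption, the nivolumab duration rule omits the interval after the last infusion: 1 and 29 days after one and two on-time infusions, against 28 and 56 days of planned cover.

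The effect on weekly dose is conditional. With the nivolumab-specific duration as denominator, the readings are 3,360, 232, 177 and 143 mg per week after 1, 2, 3 and 6 infusions, against 120 mg planned. The figure of about 8% or less under the overall duration assumes that KPT-9274 runs to Day 26 of the last cycle. If its last dose were on Day 8 of Cycle 1, the overall duration would be 8 days and the reading 480 × 7/8 = 420 mg per week.

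A reader might go on to infer that the dose-limiting toxicity rule, adverse-event capture, an efficacy endpoint or the sample size is affected. None of them uses this variable. The consequence is confined to a descriptive exposure table in about 20 patients at the two planned Part C dose levels. Severity: minor.

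**What to change.** Make two changes to SAP 3.4, for nivolumab only.

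1. Define duration of exposure as last infusion date minus first infusion date plus 28 days, capped at death or data cut-off.
2. State that average weekly nivolumab dose is total dose divided by (last infusion date − first infusion date + 28)/7 weeks.

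The second formula is left uncapped on purpose. A patient who dies 10 days after a single infusion has 11 days counted inclusively, and a capped denominator would again give an inflated 480 × 7/11 = 305 mg per week. Without the cap, on-time dosing reads 480k ÷ (28k/7) = 120 mg per week for any number of infusions.

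Leave the KPT-9274 and niacin duration rule as it is. Its effect over complete cycles is small: about 8% after one and about 1% after six. It is larger after very early stopping (a single 30 mg dose gives 30 × 7 = 210 mg per week against 90), but the obvious replacements disagree there. After doses on Days 1 and 3 only, crediting time to the end of the cycle gives 2/(28/7) = 0.5 doses per week, while crediting it up to the next planned dose on Day 5 gives 2/(4/7) = 3.5.

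The cost is one SAP definition and one program change. These are reporting definitions only, and no dosing or clinical rule is touched.
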